This stage is a group sequential statistical design, and the statistical hypothesis test will be performed at 1-sided of overall 0.025 significant level for efficacy endpoints. Trial sample size is based on the primary efficacy endpoint (i.e. sustained MG-ADL response rate within 9 weeks) in the population of AChR-Ab positive or MuSK-Ab positive patients, and the target power of the trial is 90%. An interim analysis will be performed when the first 67% (approximately 80 cases) of autoantibody-positive patients complete primary endpoint assessment. The overall class I error of statistical hypothesis testing is controlled by the Hwang-Shih-DeCani α -spending function; if statistical significance is reached at the significance level at 1-sided of 0.0063 in interim primary analysis, it can be considered that the trial is terminated prematurely (the follow-up of enrolled subjects is continued), otherwise the trial is continued, and 1-sided of 0.0230 level of significance will be applied in the final analysis. If the test for the primary endpoint is statistically significant, the sequential testing of full population will be treated at the same significance level (i.e., including both antibody-positive and antibody-negative populations). If the statistical test of full population is also statistically significant, the sequential testing will be performed at the significance level of 1-sided of 0.0159 (i.e., P Ocock Border) for remaining secondary efficacy endpoints.

The statistical hypothesis of dichotomous data will be statistically tested with normal distribution approximation, and the same normal distribution approximation will also be used for the calculation of 95% confidence interval. Missing assessments in the primary analysis will be imputed as not meeting the response threshold, and efficacy responses achieved after rescue treatment use will be treated as not meeting the efficacy response condition in the statistical analysis.

Descriptive statistics will be used for continuous data, and further analysis will be performed according to appropriate statistical analysis method (such as Kaplan-Meier, etc.).

An external independent data monitoring committee (iDMC) will be responsible for the conduct of the interim analysis and data review, and the independent data monitoring committee charter and interim statistical analysis plan (including iDMC recommended guidelines) will be finalized prior to enrollment of the first subject in Phase 3.

Phase 2 Population pharmacokinetics and dose-response analysis:

All HBM9161 plasma concentration data obtained in this phase will be used in the PopPK analysis (using nonlinear mixed effects modeling [NONMEM]) in combination of already obtained PK data if data permit, to develop a PK model to characterize the PK profiles of subcutaneous HBM9161. Individual exposure parameters for subjects will then be estimated based on established parameter estimates from the final PK model, which will be used for further dose-response (exposure-response) analyses, including PK/PD/efficacy and PK/PD/safety correlation exploratory analyses. Results of these analyses will be reported separately. The population PK/PD analysis after the end of this trial will try to provide a basis for dose selection in the phase 3 trial and determine the strategy for further trial implementation based on the analysis results.

Phase 3 Population pharmacokinetics and dose-response analysis:

The available PK and PD data for HBM9161 will be combined to develop a PopPK/PD model to further characterize the quantitative relationship between PK and/or PD and efficacy and/or safety measures. The impact of demographic characteristics, disease progression, and concomitant medications on PK and/or PD characteristics will be investigated systematically and quantitatively.

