- Percentage of patients with sustained improvement (AChR-Ab-positive or MuSK-Ab-positive patient population) during the first treatment period and observation period (baseline to Day 64): a reduction of ≥ 3 points from the baseline of Myasthenia Gravis Activities of Daily Living Scale (MG-ADL) score that persists for at least 4 weeks

Secondary study endpoints:**Clinical response assessment:**

- Percentage of patients with sustained improvement (i.e. Entire Population) during the first treatment period and observation period (Baseline to Day 64): a reduction of ≥ 3 -point from the baseline of Myasthenia Gravis Activities of Daily Living Scale (MG-ADL) score that persists for at least 4 weeks
- Percentage of patients with sustained improvement (AChR-Ab-positive or MuSK-Ab-positive patient population) during the first treatment period and observation period (baseline to Day 64): a reduction of ≥ 3 points from the baseline of Quantitative Myasthenia Gravis (QMG) score that persists for at least 4 weeks

- Percentage of the time that patients remain in clinical improvement: Percentage of the time that patients achieve clinical improvement (≥ 3 Point Reduction from Baseline for MG-ADL Score) from Baseline to Week 24 (AChR-Ab-positive or MuSK-Ab-positive Patient Population)
- Percentage of patients with minimal clinical manifestations (Minimal Symptom Manifestation, MSE) at any visit during the first treatment period and observation period (baseline to Day 64) (AChR-Ab positive or MuSK-Ab positive patient population): MG-ADL score of 0 or 1
- Percentage of patients with early improvement during the first cycle of treatment (AChR-Ab positive or MuSK-Ab positive patient population): a reduction of ≥ 3 -point of MG-ADL score at any visit from baseline to Day 15
- Percentage of patients with sustained improvement (AChR-Ab-positive or MuSK-Ab-positive patient populations) during the second treatment period and observation period: a reduction of ≥ 3 points from the baseline of MG-ADL score that persisted for at least 4 weeks

Safety Assessments:

- Overall safety profile (adverse events, laboratory tests, vital signs, etc.) of HBM9161
- Change from baseline in albumin and LDL-C levels during the study

Pharmacodynamic Assessments:

- Change of baseline in serum total IgG, serum acetylcholine receptor antibody (AChR-Ab), and muscle specific tyrosine kinase antibody (MuSK-Ab), and change in serum complement (CH50, C3)

Immunogenicity Assessment:

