12. Any active infection at the screening visit or serious infection requiring treatment with intravenous anti-infective drugs or hospitalization within 8 weeks before the screening visit.

13. Previous or current human immunodeficiency virus (HIV), hepatitis C virus (HCV) infection; subject has a positive test for any of the following at the screening visit: HCV antibody, HIV antibody type 1 and 2.

14. At the screening visit: the subject is positive for HBV surface antigen; the subject has negative HBV surface antigen and positive anti-HBV core antibody, and further test or medical documents within 12 weeks prior to screening visit confirms HBV-DNA quantitative detection > 2 000 IU/mL.

15. Previous or current infection with Mycobacterium tuberculosis (positive or indeterminate interferon gamma release test at 12 months prior to the screening visit).

16. Has acute liver injury (e.g., hepatitis) or significant cirrhosis (Child-Pugh Class C) or any of the following:

a. Alanine aminotransferase (ALT) and/or aspartate aminotransferase (AST) > 2 times the upper limit of normal (ULN) according to the laboratory reference range at the screening visit;

b. Total bilirubin > 1.5 times the upper limit of normal (ULN) at the screening visit according to the laboratory reference range.

17. Clinically significant laboratory abnormality that, in the opinion of the investigator, would pose a risk to the subject's participation in this study or interfere with study participation; or any of the following:

a. Total serum IgG at screening visit ≤ 6 g/L ;

b. Serum albumin < 3.5 g/dL at the screening visit;

c. Blood neutrophils < $1.5 \times 10^9/L$ at the screening visit;

d. Blood calcium values more than 5% of the normal range.

18. Significant cardiovascular (including serious cardiac arrhythmias), hepatic, renal, respiratory, endocrine, or hematologic disease, or other medical or psychiatric condition that, in the opinion of the investigator, would preclude the subject from participating in the study or would require hospitalization during the study.

19. Malignancy at any time, including malignant thymoma, bone marrow or lymphodysplastic disease, etc.

20. Men with QTcF interval > 450 msec and women with > 470 msec (one retest is allowed to determine eligibility).

21. Alcohol or drug dependence/abuse at present or during past one year, except nicotine and coffee.

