 - Double contraception: condom or cervical cap (diaphragm or cervical cap) plus spermicide (foam/gel/cream/suppository); or
 - An intrauterine device, implanted by a qualified physician; or

- Estrogen vaginal ring; or
- Contraceptive patch.

4. Male subjects must use effective contraceptive methods or have their heterosexual partners use effective contraceptive methods during their participation in this clinical trial.

5. Meets MGFA myasthenia gravis clinical classification IIa-IVa (includes types IIa, IIb, IIIa, IIIb, and IVa) at the screening visit and at the baseline visit.

6. Positive or negative AchR-Ab/MUSK-Ab at the screening visit and meets at least 1 of the following 3 criteria:

- a. Repeated electrical stimulation indicates neuromuscular junction transmission disorder (including medical history record);
- b. Positive Tensilon test or neostigmine test (including medical history record);
- c. The patient's MG symptoms improve after treatment with oral cholinesterase inhibitors at the judge of the physician.

7. MG-ADL score ≥ 5 and eye muscle-related score less than 50% of the total score at screening visit and baseline visit.

8. QMG score ≥ 11 at screening visit and baseline visit.

9. Subjects with stable treatment for myasthenia gravis at the randomization visit (Visit 2), where stable treatment is defined as follows (at least one is used):

- a. Cholinesterase inhibitors: stable dose for more than 4 weeks at randomization visit; and suspended for more than 12 hours when all clinical assessments are conducted;
- b. Corticosteroids: start at least 3 months prior to randomization visit and stable for at least 1 month at randomization visit (The total daily dose of glucocorticoids should not exceed prednisone 40 mg or equivalent) ;
- c. Immunosuppressants:
 - Azathioprine: start at least 12 months prior to the randomization visit and stable for at least 4 months at the randomization visit.
 - Other immunosuppressive drugs (e.g., cyclophosphamide, cyclosporine A, tacrolimus, mofetil, methotrexate, etc.): start at least 6 months prior to the randomization visit and at a stable dose for at least 3 months at the randomization visit.

10. If taking a statin, a medical history is required to document that the dose and regimen have been stable for 2 months prior to the Screening Visit.

11. Subject is willing and able to modify current disease therapy per protocol requirements at the discretion of the investigator.

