13. Any active infection at the Screening Visit or serious infection requiring treatment with intravenous anti-infective drugs or hospitalization within 8 weeks before the Screening Visit.

14. Previous or current human immunodeficiency virus (HIV), hepatitis C virus (HCV) infection; subject has a positive test for any of the following at the Screening Visit: HCV antibody, HIV antibody type 1 and 2.

15. At the screening visit: subjects with positive HBV surface antigen who did not receive treatment; subjects with positive HBV surface antigen who had received standard antiviral therapy (recommended to use Entecavir) for at least 2 weeks before the first dose of study drug (confirmed by medical documents) and promised to continue antiviral therapy during the study and 6 months after drug withdrawal; subjects without liver fibrosis or cirrhosis shown by abdominal B ultrasound (confirmed by medical documents if B ultrasound results within 30 days after drug withdrawal) can be excluded; subjects with negative HBV surface antigen and positive anti-HBV core antibody should be confirmed by quantitative detection of HBV-DNA ≤ 2000 IU/mL (confirmed by medical documents at screening visit or 12 weeks before screening visit).

16. Previous or current infection with Mycobacterium tuberculosis (positive interferon gamma release test 12 weeks before screening visit).

17. Has acute liver injury (eg, hepatitis) or significant cirrhosis (Child-Pugh Class C) or any of the following:

a. Alanine aminotransferase (ALT) and/or aspartate aminotransferase (AST) > 2 times the upper limit of normal (ULN) according to the laboratory reference ranges at the screening visit

b. Total bilirubin > 1.5 times the upper limit of normal (ULN) at the screening visit according to the laboratory reference range.

18. Clinically significant laboratory abnormality that, in the opinion of the investigator, would pose a risk to the subject's participation in this study or interfere with study participation; or any of the following:

a. Serum total IgG ≤ 6 g/L at screening visit;

b. Serum albumin < 3.5 g/dL at the screening visit;

c. Blood neutrophils $< 1.5 \times 10^9/L$ at the screening visit;

d. Blood calcium (or corrected calcium) values exceeding 5% of the normal range.

e. Serum LDL-C ≥ 4.9 mg/dL; subjects may be treated with lipid-lowering drugs prior to starting study medication, (Recommended use of ezelpfos for lipid-lowering drugs),who can be enrolled.

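### Phase 3 exclusion 18e prints an LDL-C limit (4.9 mg/dL) that practically every adult exceeds; secondarily, exclusion 15 uses a verb of exclusion where an exemption must be meant

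*Protocol*

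**What the plan says.** **LDL-C.** In the protocol's Phase 3 exclusion criteria, item 18 bars subjects with a laboratory abnormality that worries the investigator, or with any one of five listed results. The fifth, 18e, is "Serum LDL-C ≥ 4.9 mg/dL". A rider follows: "subjects may be treated with lipid-lowering drugs prior to starting study medication", and such subjects may then be enrolled. It adds a drug recommendation, "Recommended use of ezelpfos for lipid-lowering drugs", whose drug name cannot be read in the text at hand. The corresponding Phase 2 item, exclusion 17, ends at 17d, "Blood calcium values more than 5% of the normal range", and has no LDL-C limit. The Phase 3 Safety Assessments include "Change from baseline in albumin and LDL-C levels during the study".

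**Hepatitis B.** Phase 3 exclusion 15 runs through four clauses divided by semicolons:

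1. "subjects with positive HBV surface antigen who did not receive treatment".
2. Surface-antigen-positive subjects on standard antivirals for at least 2 weeks before the first dose, who have "promised to continue antiviral therapy during the study and 6 months after drug withdrawal".
3. Subjects whose abdominal ultrasound shows no fibrosis or cirrhosis. This clause carries a 30-day window counted from drug withdrawal and closes with a verb of exclusion.
4. Subjects who are surface-antigen negative and anti-core positive, who must have documented HBV-DNA of at most 2000 IU/mL.

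**The concern.** An LDL-C exclusion stated as at or above some value is an upper limit, meant to keep out subjects with high LDL-C. A limit of 4.9 mg/dL lies far below any ordinary adult value, so it cannot separate high from normal. It stands as a numerical criterion of its own for a confirmatory phase of about 144 planned subjects. As printed, any enrolled subject above 4.9 mg/dL and not on a lipid-lowering drug is an eligibility deviation on paper. LDL-C is also a measure the sponsor chose to follow for safety.

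In exclusion 15 the wording works against its own conditions. It demands a commitment to antiviral treatment for the length of the study, which only an enrolled subject can keep, and then attaches a verb of exclusion to a healthy-looking liver. A site that follows the text literally would turn away subjects the sponsor appears to want.

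**Working it through.** **LDL-C: inputs**
- Printed limit: 4.9 mg/dL (Phase 3 exclusion 18e).
- Conversion factor: 38.67 mg/dL per mmol/L of cholesterol, tried over 38.6 to 38.7. This is an assumption; the protocol gives no factor.
- Adult LDL-C of roughly 40 to 190 mg/dL. This is also an assumption, used only for scale.

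**Step 1, the printed limit in mmol/L** (mg/dL divided by the factor)
- 4.9 / 38.67 = 0.1267 mmol/L
- 4.9 / 38.7 = 0.1266; 4.9 / 38.6 = 0.1269

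**Step 2, the printed limit against ordinary values**
- 40 / 4.9 = 8.2 and 190 / 4.9 = 38.8

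Even the low end of the assumed range is about eight times the limit, so the conclusion does not hang on where that range is drawn.

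**Step 3, which unit makes 4.9 sensible**
- As mmol/L: 4.9 × 38.67 = 189.5 mg/dL (4.9 × 38.6 = 189.1; 4.9 × 38.7 = 189.6). This is plausible as a high-LDL-C cut-off, and 38.67 times the printed limit.
- As g/L: 490 mg/dL, or 490 / 38.67 = 12.7 mmol/L. This is not a sensible cut-off.

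Of these readings mmol/L is the natural one. No other LDL-C figure in the document confirms it, and Phase 2 has none to copy.

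**Exclusion 15: the texts side by side**

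| Place | Effect |
|---|---|
| Phase 2 exclusion 14 | Every surface-antigen-positive subject is excluded |
| Phase 3 exclusion 15, first clause | Narrowed to untreated positive subjects |
| Phase 3 exclusion 15, second clause | Treated positive subjects: at least 2 weeks of therapy, commitment through the study and 6 months beyond |
| Phase 3 exclusion 15, third clause | No fibrosis or cirrhosis on ultrasound; verb of exclusion |
| Phase 3 exclusion 21 | A condition, then imaging with a 30-day limit and medical documents; verb of inclusion |

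- Splitting treated from untreated subjects has no purpose if both are excluded.
- A commitment to keep taking antivirals in the study makes sense only for someone who enters it.
- Taken alone, the third clause excludes subjects because their livers look normal.
- Exclusion 21 has the same build and ends the way exclusion 15 evidently should.
- Drug withdrawal comes after treatment, so a scan window counted from it cannot be applied at screening.

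The HBV-DNA condition is not at fault. Phase 2 excludes above 2000 IU/mL and Phase 3 requires at most 2000 IU/mL, which is the same cut-off.

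**The case against.** The best case on the other side is that these are drafting slips, probably from translation, and easily noticed. The wording elsewhere shows similar marks, and the Phase 2 statistical section refers to a main body of the protocol that is not shown and may hold correct text. Sites may also work from an original-language version. All of this limits the practical harm. It does not make the printed text right. The number, unit and sentence in 18e are intact, and reading a PDF does not turn mmol/L into mg/dL.

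A reader might infer more than the document supports:

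- *That nobody could be enrolled.* The rider admits subjects treated with lipid-lowering drugs, and the slip is plain enough that sites would probably spot it.
- *That sites would have to invent their own limit.* They can ask the sponsor.
- *That the limit fixes the starting range for the LDL-C safety measure.* The rider admits treated subjects with no stated ceiling, so even a corrected limit would not bound baseline LDL-C. Phase 3 is randomized and placebo-controlled, so the comparison between arms remains.
- *That the rider contradicts inclusion 10.* That criterion asks statin users to "document that the dose and regimen have been stable for 2 months prior to the Screening Visit". It concerns statins only. The recommended drug's name is unreadable, so its class is unknown and no contradiction is shown.
- *That exclusion 15 says in terms that treated positive subjects are excluded.* A semicolon separates the clause on treated subjects from the verb of exclusion. Joining the two is an inference, though the only one that makes sense of the criterion.
- *That exclusion 15 leaves a serious gap for treated subjects with liver disease or short therapy.* Any such gap arises only under a repaired reading. Exclusions 1, 17 and 19 and inclusion 13 still apply.

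**Conclusion.** The LDL-C limit in Phase 3 exclusion 18e is wrong as printed. At about 0.127 mmol/L (0.1266 to 0.1269 over the assumed factors) practically every adult exceeds it, and it cannot serve as a screen for high LDL-C. That figure and unit cannot both be right is firm. That 4.9 mmol/L (about 190 mg/dL) was intended is probable but remains for the sponsor to confirm.

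Exclusion 15 is defective in wording. Its conditions are conditions for entry, its verb says the opposite, and its ultrasound window cannot be applied at screening. It has no numerical effect.

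Both are errors of eligibility drafting. Neither touches alpha, power, sample size or the planned analysis. The judgment rests on the text shown and would need revisiting against the main body. If that is correct, the text shown contradicts it and should be brought into line.

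**What to change.** **18e.** Restate the limit, probably as LDL-C ≥ 4.9 mmol/L (about 190 mg/dL) at the screening visit, once the sponsor has confirmed the figure.

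**15.** Exclude all surface-antigen-positive subjects except those who meet every one of these conditions:
1. documented standard antiviral therapy for at least 2 weeks before the first dose;
2. a commitment to continue it during the study and for 6 months after drug withdrawal;
3. no fibrosis or cirrhosis on an abdominal ultrasound dated relative to screening.

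Keep the requirement of HBV-DNA ≤ 2000 IU/mL for surface-antigen-negative, anti-core-positive subjects.

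The cost is close to nothing: one unit, one reworded criterion, and matching updates to the eligibility checklist and any electronic check. Design, sample size and analysis stay as they are.

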This phase is a randomized, double-blind, placebo-controlled, parallel-group, group sequential design. Trial procedures include screening period (2 weeks), first treatment period (6 weeks), observation period (4 weeks), individualized follow-up period (until the patient meets the criteria for re-treatment), second treatment period (6 weeks), observation period (4 weeks) and follow-up period (to 5 weeks after last dose of study drug or to Week 24, which occurs later); the total length of the double-blind period will be at least 24 weeks up to 28 weeks. The latest start of

retreatment in this study phase will be Day 127 (Week 18). Subjects will be dosed for up to two treatment cycles throughout the study. Subjects who complete this study will have access to enter an open-label extension trial (separate protocol) to receive open-label HBM9161 Treatment.

[figure not shown]
A total of 120 subjects with positive AChR-Ab or MuSK-Ab and up to 24 subjects with negative AChR-Ab and MuSK-Ab are planned for this phase (The randomization will end after approximately 120 subjects with positive serum AchR-Ab or MUSK-Ab are enrolled) and randomized into 2 treatment regimens in a 1:1 ratio. Arm 1 will receive HBM9161 680 mg; Arm 2 will receive placebo. Whether or not AChR-Ab or MuSK-Ab is positive, and whether or not concomitant steroids are used will be randomization stratification factors.

First, eligible subjects will be screened into the double-blind treatment phase and blindly assigned to receive either HBM9161 680 mg or placebo for the first treatment period, administered once weekly (QW) for 6 doses, followed by an observational follow-up of at least 4 weeks for the primary endpoint analysis on Day 64.

Subjects who complete the first treatment period will start the administration of the second treatment period if they meet the dosing criteria for the second treatment period at Week 9. Otherwise they will be followed individually until they require a second cycle of therapy or until Week 24.

The second treatment period will be administered once weekly (QW) for a total of 6 doses in the first treatment period, followed by an observation period (4 weeks) and a follow-up period (5 weeks after the last dose of study drug or until Week 24 (which occurs later). Subjects will be dosed for up to two treatment cycles during the study, with the start of the second treatment period no later than Day 127 (i.e. Week 18).

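### Does the single level of 0.0159 for the remaining Phase 3 secondary endpoints let the later-maturing ones exceed one-sided 0.025?

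*Protocol*

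**What the plan says.** The Phase 3 Statistical Methods section of the protocol sets the frame: "the statistical hypothesis test will be performed at 1-sided of overall 0.025 significant level for efficacy endpoints". The interim is tied to the primary endpoint: "An interim analysis will be performed when the first 67% (approximately 80 cases) of autoantibody-positive patients complete primary endpoint assessment". The primary error is "controlled by the Hwang-Shih-DeCani α -spending function", with nominal one-sided levels of 0.0063 at the interim and 0.0230 at the final analysis. The full-population test follows at the same level as the primary. After that, "sequential testing will be performed at the significance level of 1-sided of 0.0159 (i.e., P Ocock Border) for remaining secondary efficacy endpoints".

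On success at the interim, "it can be considered that the trial is terminated prematurely (the follow-up of enrolled subjects is continued"; otherwise the trial goes on to the final analysis.

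Five secondary efficacy endpoints remain after the full-population test (Phase 3 study endpoints). Three are complete by Day 64 or earlier: sustained QMG improvement, minimal symptoms and early improvement by Day 15. Two mature later. One is the percentage of time in clinical improvement, "from Baseline to Week 24 (AChR-Ab-positive or MuSK-Ab-positive Patient Population". The other is "Percentage of patients with sustained improvement (AChR-Ab-positive or MuSK-Ab-positive patient populations) during the second treatment period and observation period". The second cycle begins after Day 64 at the earliest, "with the start of the second treatment period no later than Day 127" (Phase 3 study design).

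The section does not state at which look or looks each remaining secondary endpoint is tested. It announces an interim statistical analysis plan, to be final before the first Phase 3 subject is enrolled.

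**The concern.** A Pocock level is valid for a given information fraction. The 67% here is the fraction of antibody-positive subjects with a Day 64 outcome, yet the one level serves every remaining secondary endpoint. A subject who has just reached Day 64 has neither a Week 24 nor a second-cycle outcome, so with 120 enrolled those two endpoints must stand below 67% at the interim. The lower the fraction, the weaker the correlation between the two looks, and the more error two tests at 0.0159 spend.

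The text seems to leave room for two tests. Stopping after an interim success is optional, and follow-up of enrolled subjects continues, so a fuller data set on these endpoints will arise later. At stake would be the error rate behind the statements on durability of effect and on retreatment. The primary endpoint would not be touched.

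**Working it through.** **1. Reproduce the plan's figures.** Inputs from Phase 3 Statistical Methods: one-sided 0.025, interim at 67% (80/120 = 2/3), levels 0.0063, 0.0230 and 0.0159. With two looks, the test statistics are bivariate normal with correlation √t, where t is the information fraction at the interim. The error of two tests at levels p1 and p2 is

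E(p1, p2, t) = 1 − Φ₂(z(1−p1), z(1−p2); √t).

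- Solving E(p, p, t) = 0.025 gives p = 0.01591 at t = 2/3 and 0.01594 at t = 0.67. The stated 0.0159 reproduces.
- Hwang-Shih-DeCani spending with parameter −4 (not stated in the protocol, but it fits) at t = 0.67 gives 0.00634 and 0.02302. The stated 0.0063 and 0.0230 reproduce.

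**2. Error if a late endpoint were tested at 0.0159 at both looks.**

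| Endpoint's own t at interim | Error |
|---|---|
| 2/3 | 0.0250 |
| 0.50 | 0.0270 |
| 0.40 | 0.0280 |
| 0.30 | 0.0289 |
| limit, t → 0 | 1 − (1 − 0.0159)² = 0.0315 |

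The protocol gives no accrual rate, so a range is assumed. Week 24 is 15 weeks after Day 64 (Week 9). With steady accrual of r antibody-positive subjects per week and 120 enrolled, t = (80 − 15r)/120. For r = 1, 2, 3 and 4 this is 0.54, 0.42, 0.29 and 0.17, and the error is 0.0265, 0.0278, 0.0290 and 0.0300. These are upper bounds, approached when every preceding test is nearly certain to pass at the interim.

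**3. Error if each late endpoint is tested once.** The simulation uses a true null for the secondary endpoint, gated behind a primary tested at 0.0063 and 0.0230, with the maximum taken over the size of the primary effect.

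- Tested at the look where the primary succeeds: about 0.016 to 0.017 for t = 0.2 to 0.5, and 0.021 at t = 0.67 (correlation with the primary up to 0.95).
- Tested once on complete follow-up of those enrolled, with enrolment either stopped after the interim (final number 90 to 107) or taken to 120: at most about 0.020 (correlation up to 1.0).

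All are below 0.025. They can exceed 0.0159 because the primary result decides which data set is used.

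**4. Which case does the text describe?** If the primary fails at the interim, the gate is closed and the secondary endpoints can be tested only at the final analysis: one test. If it succeeds, the protocol keeps enrolled subjects under follow-up, which fits one analysis of the late endpoints when their data are complete. No sentence calls for testing them on partial data at the interim and then again.

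**The case for a change.** The best counter-argument is the label. A Pocock boundary is by construction a level for repeated looks, one number is fixed for all five endpoints, and nothing forbids a second test after an interim success. At the effect giving 90% power, the primary passes at the interim with probability 1 − Φ(2.495 − 3.277·√(2/3)) = 0.57, so the situation is not rare.

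The calculation in this argument stands, and a plan that did prescribe 0.0159 at both looks for these two endpoints would have a small but real excess. Two parts do not carry over.

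First, the label does not imply two tests of the same endpoint. Even a single gated test needs a level below 0.025 when the primary result decides at which look it is done. The 0.021 in step 3 arises in exactly that way, and 0.0159 covers it.

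Second, 0.57 concerns the primary alone. A late endpoint is reached at the interim only if the full-population test and the earlier secondary tests pass there too. Taking the listed order as the testing order, the same design effect on each endpoint and a common correlation of 0.3, 0.5 or 0.7, everything ahead of the Week 24 endpoint passes with probability 31%, 36% or 42%. Error control is a worst-case standard, so this does not excuse inflation, but it does show that the figures in step 2 are ceilings.

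The Week 24 endpoint is also a continuous percentage of time. The section promises descriptive statistics for continuous data, plus further analysis it does not specify, so a formal test of it at two looks is a further assumption.

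**Conclusion.** The concern does not hold. The level 0.0159 is correctly computed for the design that the protocol describes, and it is adequate for the endpoints that mature by Day 64. For the Week 24 and second-cycle endpoints, an error above 0.025 (0.0270 at 50% information, never above 0.0315) requires tests at both looks, which the protocol does not state. With one test per endpoint, the simulated error is at most about 0.021, so the overall 0.025 is respected.

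This rests on reading the protocol as not prescribing a second test, and on simulations with gate levels 0.0063 and 0.0230 and a broad range of correlations and primary effects. What remains is that the text does not assign a look to each late endpoint. That detail commonly sits in the statistical analysis plan, or in the interim plan that the protocol announces, and its absence here does not make any stated number or rule wrong.
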